SAEs that are related to the study vaccine will be collected and recorded from the time of the first receipt of study vaccine until the subject is discharged from the study.

In addition to the above-mentioned reporting requirements and in order to fulfil international reporting obligations, SAEs that are related to study participation (i.e. protocol-mandated procedures, invasive tests, a change from existing therapy) or are related to a concurrent ***GSK-GlaxoSmithKline*** medication/vaccine will be collected and recorded from the time the subject consents to participate in the study until she/he is discharged from the study.

The time period for collecting and recording pregnancies will begin at the first receipt of study vaccine until study end. See section 12.5.9 for instructions on reporting of pregnancies. This applies **only** to pregnancy cases with exposure to ***the study treatment Shingrix*** at any age of gestation. The timing of exposure to ***the study treatment Shingrix*** during pregnancy is estimated in relation to the first day of the last menstrual period, ultrasound or known date of fertilization (e.g., assisted reproductive technology).

The time period for collecting and recording of pIMDs will begin at the first receipt of study vaccine and will end 12 months following administration of the last dose of study vaccine. ***Beyond this time period, only serious pIMDs that are related to the study vaccine are to be reported.*** See section 12.5.9.5 for instructions on reporting of pIMDs.

Section 12.5.9.5 Reporting of pIMD to GSK

The seriousness assessment of the pIMDs will use the same criteria as apply for SAEs (see Section 12.5.2).

Section 12.8. Appendix 8: Protocol Amendment History

eTrack study number and Abbreviated Title	204939 (ZOSTER-062) 212884 (ZOSTER-076)
IND number	BB-IND-13857
EudraCT number	2016-000744-34
Amendment number:	Amendment 1

RAPIDO DV	Reporting & Analysis Plan Improving Design and Delivery of Outputs Data Viewer
RR	Relative Risk
RZV	Recombinant Zoster Vaccine
SAE	Serious adverse event
SAP	Statistical Analysis Plan
SBIR	GSK Biological's Internet Randomisation System
SD	Standard Deviation
SDTM	Study Data Tabulation Model
SR	Study Report
TFL	Tables Figures and Listings
TOC	Table of Content
VE	Vaccine Efficacy
YOA	Years of Age

1. DOCUMENT HISTORY

Date	Description	Protocol Version
08 FEB 2021	Initial Version	Amendment 2 Final: 23 NOV 2020
10 May 2023	
Amendment 1: Following are the changes from SAP from 08 FEB 2021:-
 
 • Added RAPIDO DV • Added analysis of deviation from protocol-defined age and visit interval on ES. • Updated model of vaccine efficacy: added by agecat statement and removed agecat from model. • Substituted kaplan meier curves by cumulative incidence curves. • Calculation and derivation rule for some solicited adverse event grade 4 and duration has been added • Related grade 1 and related grade 2 have been added to GSK and Chinese scale analyses. • Substituted 'grade 3' by at 'least grade 3' in solicited local and solicited general summaries based on GSK scale. Also, added the categories that will be displayed for fever in solicited general summaries • Update of grade 3 definition for redness and swelling based on Chinese scale • Update of the Preferred Terms used to determine grade 4 for Redness and Swelling. • Update in handling of missing data in section 10.1.2.3.2 • Analysis for secondary safety endpoint related to 'SAE due to study participation and GSK concomitant medication/vaccination' has been added. • Analysis of concomitant medication related to confirmed HZ episode has been added • Covid-19 related analyses have been added • Minor edits in text for clarification. • Added site specific Covid-19 pandemic measure periods 	Amendment 2 Final: 23 NOV 2020

2. OBJECTIVES/ENDPOINTS

[figure not shown]
Below are the study objectives and endpoints:-

Objectives	Endpoints

To evaluate vaccine efficacy (VE) in the prevention of HZ compared to placebo in Chinese adults ≥ 50 YOA, as measured by the reduction in herpes zoster (HZ) risk.
 
Criterion: The objective is met if the lower limit (LL) of the 2-sided 95% confidence interval (CI) of VE is above 25%.
	
Primary
 
Confirmed HZ cases in the modified Exposed Set (mES).

To evaluate VE in the prevention of HZ compared to placebo in subjects within each of the following age ranges: 50-69 years of age (YOA) and ≥ 70 YOA, as measured by the reduction in HZ risk
	
Secondary
 
Confirmed HZ cases within each of the following age ranges: 50-69 YOA and ≥ 70 YOA in the mES.

To evaluate vaccine reactogenicity and safety
	
Solicited local and general adverse events (AEs)
 
 Occurrence, intensity and resulting in medically attended visit of each solicited local AE within 7 days (Days 1 – 7) after each vaccination Occurrence, intensity and resulting in medically attended visit and relationship to vaccination of each solicited general AE within 7 days (Days 1 – 7) after each vaccination. 
Unsolicited AEs
 
 Occurrence, intensity, resulting in a medically-attended visit, and relationship to vaccination of unsolicited AEs (including cellulitis) within 30 days (Days 1 – 30) post-vaccination period, according to the Medical Dictionary for Regulatory Activities (MedDRA) classification. 
Serious Adverse Events (SAEs)
 
 Occurrence and relationship to vaccination of SAEs from Day 1 up to 30 days post last vaccination.

Objectives	Endpoints
	
 • Occurrence and relationship to vaccination of SAEs from Day 1 up to 12 months post last vaccination. • Occurrence of SAEs related to study vaccine, from Day 1 up to end of study. • Occurrence of SAEs related to study participation or to GlaxoSmithKline concomitant medication/vaccine, from Day 1 up to end of study. • Occurrence and relationship to vaccination of fatal SAEs from Day 1 up to 30 days post last vaccination. • Occurrence and relationship to vaccination of fatal SAEs from Day 1 up to 12 months post last vaccination. • Occurrence of related-fatal SAEs from Day 1 up to end of study. 
potential Immune-Mediated Diseases (pIMDs)
 
 • Occurrence and relationship to vaccination of pIMDs from Day 1 up to 30 days post last vaccination. • Occurrence and relationship to vaccination of pIMDs from Day 1 up to 12 months post last vaccination. • Occurrence of related serious pIMDs after 12 months post last vaccination up to study end.
Exploratory	CCI

3. STUDY DESIGN

Figure 1 Study design overview

CC1 [REDACTED]; N= number of subjects planned to be enrolled; Vacc= Vaccination
RZV= Recombinant Zoster Vaccine

CC1 [REDACTED]
‡ All subjects will be followed-up until last enrolled subject has completed 1 year of follow-up post last vaccination. In case criteria for vaccine efficacy analyses are not met during this period, the follow-up will be extended.

- **Experimental design:** Phase IV, randomized, observer-blind, placebo-controlled, multi-centric, single-country study with 2 parallel groups.
- **Duration of the study:** The duration of the study will vary for each subject. The duration of the study will be up to the study conclusion contact that occurs within 30 days of the projected study conclusion date of the last enrolled subject, that is, 14 months (approximately 430 days) from the enrolment date. Therefore, subjects enrolled early in the trial will be followed for longer duration than the subjects who enrol later in the trial. In case criteria for VE analyses are not met during this period, the follow-up will be extended.

The study conclusion visit/ contact for subjects with an ongoing episode of HZ at the time of last subject last contact will occur at Visit HZ-5 (Day HZ-29).

- **Epoch 001 (Vaccination phase):** Starting at Visit 1 (Day 1) until Visit 3 (Month 3) at one month post last vaccination.
- **Epoch 002 (Follow-up phase):** Starting with the first monthly contact after Visit 3 (Month 3) and ending at the monthly contact that occurs within 30 days of the projected study conclusion date of the last enrolled subject, that is, 14 months (approximately 430 days) from the enrolment date of the last enrolled subject.
- **Primary completion Date (PCD):** The primary completion date will be when the last subject completes his/her study conclusion contact (within 30 days of the projected study conclusion date of the last enrolled subject, that is, 14 months (approximately 430 days) from the enrolment date. In case criteria for VE analyses are not met during this period, the follow-up will be extended.

- **End of Study (EoS):** 1) After all the subjects complete their study conclusion contact, occurring within 30 days of the projected study conclusion date of the last enrolled subject, that is, 14 months (approximately 430 days) from the enrolment date of the last subject; In case criteria for VE analyses are not met during this period, the follow-up will be extended and 2) the release of all polymerase chain reaction (PCR) test results for the HZ rash lesion samples. Refer to section 7.1 for more detail.
- **Control:** placebo controlled
- **Vaccination schedule:** 0 and 2 months
- **Treatment allocation:** Eligible subjects will be randomized (1:1) to RZV group or Placebo group. The randomization algorithm will use a stratification procedure accounting for age (50-69 YOA and \geq 70 YOA).
- **Sampling schedule:**
 - CCI [REDACTED]
 - [REDACTED]
 - [REDACTED]
 - Clinical specimens of HZ lesions will be collected from all subjects who are clinically diagnosed with a suspected case of HZ (Section 8.3.2 of the protocol).
 - A urine specimen will be collected from all female subjects of child-bearing potential (see glossary of terms in the protocol definition of woman of child bearing potential) at Visit 1 (Day 1) and Visit 2 (Month 2).
- **Study group and treatment number allocation:** The target will be to enrol approximately 6138 eligible subjects who will be randomly assigned to 2 study groups in a (1:1) ratio (approximately 3069 subjects in each group).

The enrolment will be performed to ensure distribution of the population across the 2 age strata (50-69 YOA and \geq 70 YOA). Approximately 75-80% and 20-25% subject should be enrolled in 50-69 YOA and \geq 70 YOA, respectively. The expected distribution of subjects within these 2 age strata is as shown in [Table 1](#).

To ensure that the collection of date of birth will not jeopardize the privacy of Personally Identifiable Information (PII), only year of birth (YYYY) will be collected.

Table 1 Number of subjects required for enrolment

Age Stratum	Vaccine	Targeted number (%) of subjects
50-69 YOA	RZV	4604-4910 (75-80%)
	Placebo	
\geq 70 YOA	RZV	1228-1534 (20-25%)
	Placebo	

Allocation of the subject to a study group at the investigator site will be performed using a randomization system on internet (SBIR). Within each age stratum, the randomization algorithm will use a minimization procedure accounting for center, gender, age (50-59, 60-69, 70-79 and \geq 80 YOA) and a combined minimization factor to reflect the presence of any of the following conditions: type 2 diabetes mellitus, asthma, chronic obstructive pulmonary disease, chronic kidney disease and depression. Minimization factors will have equal weight in the minimization algorithm.

- Allocation of subjects to assay subsets - **CCI**

4. ANALYSIS SETS

4.1. Definition

4.1.1. Enrolled Set

The enrolled set will include all eligible subjects who have signed an informed consent and were randomized or undergone an invasive procedure.

4.1.2. Exposed Set

Exposed Set (ES) will include all subjects who receive at least 1 dose of the study treatment. The allocation in a group is done in function of the administered treatment.

The ES for the analysis of solicited AEs will include all participants who received at least 1 dose of the study treatment and who have documented solicited AEs (i.e. diary card for solicited AEs completed and returned).

The ES for the analysis of any other AEs other than solicited AEs will include all participants who received at least 1 dose of the study treatment.

4.1.3. Modified Exposed Set

The modified Exposed Set (mES) excludes subjects from the ES who were not administered 2 doses of the study treatment per protocol, or who developed a confirmed case of HZ prior to 30 days after the second vaccination (Refer to section 4.2.3 for more detail on the criteria).

4.1.4. Per Protocol Set

All subjects who received at least 1 dose of the study treatment to which they are randomised and have post-vaccination data minus subjects with protocol deviations that lead to exclusion. The Per Protocol Set (PPS) (in vaccinated subjects) will include all evaluable vaccinated subjects:

- **CCI** [REDACTED];
- who have received 2 doses of study vaccine;
- for whom the study vaccine has been administered as per protocol;
- who have not received medication/vaccine forbidden in the protocol (refer to Section 4.2.4 for details on the criteria);
- who meet all eligibility criteria (refer to Sections 6.1 and 6.2 of the protocol);
- who comply with the procedures and intervals defined in the protocol;
- who do not meet any of the criteria for elimination during the study (refer to Section 4.2.4 for details on the criteria);
- for whom data concerning immunogenicity endpoint measures are available.

The intervals allowed for the inclusion in the PPS is the ‘allowed interval per protocol’ as defined in following table:

Table 2 Intervals between study visits applicable for PPS

Interval	Optimal length of interval	Allowed interval per protocol
Visit 1→Visit 2	60 days (2 months)	49 days - 83 days
Visit 2→Visit 3	30 days (1 month)	28 days - 48 days

4.2. Criteria for eliminating data from Analysis Sets

Elimination codes are used to identify subjects to be eliminated from analysis. Detail is provided below for each set.

4.2.1. Elimination from Enrolled Set

Code 800 (fraudulent data), 900 (invalid ICF) and 1010 (treatment number not allocated) will be used for identifying subjects eliminated from Enrolled Set.

4.2.2. Elimination from Exposed Set (ES)

Code 1030 (Study treatment not administered at all), 800 (fraudulent data), **900 (invalid ICF)** and 1010 (treatment number not allocated) will be used for identifying subjects eliminated from ES.

4.2.3. Elimination from modified Exposed Set (mES)

Code 1030 (Study treatment not administered at all), 800 (fraudulent data), **900 (invalid ICF)**, 1010 (treatment number not allocated), 1070 (treatment not administered according to protocol), 2500 (Subject who didn't receive two doses) and 3500 (Subject having confirmed HZ episode prior to 30 days after the dose 2) will be used for identifying subjects eliminated from mES.

Please note that impact of COVID-19 on the modified Exposed Set for vaccine efficacy analysis will be determined on a case-by-case basis.

4.2.3.1. Excluded subjects

A subject will be excluded from the mES analysis under the following conditions. Please note that impact of COVID 19 on the mES will be determined on a case-by-case basis.

Code	Condition under which the code is used	Visit (timepoints) where the code is applicable
800	Fraudulent data	All
900	Invalid ICF	Visit 1
1010	Treatment number not allocated	Visit 1
1030	Study vaccine not administered at all	Visit 1
1070**	Vaccination not according to protocol: 
 Subjects got vaccinated with the correct vaccine but containing a lower volume Administration not according to protocol for reason specified by investigator other than route, side and site. Site and route of vaccination is wrong or unknown Wrong replacement or study vaccine administered (not compatible with the vaccine regimen associated to the treatment number) 	Visit 1, Visit 2
2500	Subjects who didn't receive two doses	Visit 2
3500	Subjects having confirmed HZ episode prior to 30 days after the dose 2	Visit 1 to Visit 3

** Attribution of these elimination codes will be evaluated on case-by-case basis and requires CRDL confirmation

4.2.4. Elimination from Per-protocol analysis Set (PPS)

4.2.4.1. Excluded subjects

A subject will be excluded from the PPS analysis under the following conditions. Please note that impact of COVID 19 on the per protocol set will be determined on a case-by-case basis.

Code	Condition under which the code is used	Visit (timepoints) where the code is applicable
800	Fraudulent data	All
900	Invalid ICF	Visit 1
1010	Treatment number not allocated	Visit 1
1030	Study vaccine not administered at all	Visit 1
1040*	Administration of concomitant vaccine(s) forbidden in the protocol Any concomitant vaccination not foreseen by the study protocol administered in the period starting 30 days before the first dose of the study vaccine and ending at Visit 3 (Day -30 to Month 3)	- 30 days to Visit 1 through Visit 3
1050	Randomisation failure	All
1060	Randomisation code was broken	Visit 1 to Visit 3
1070**	Vaccination not according to protocol: 
 Subjects got vaccinated with the correct vaccine but containing a lower volume Administration not according to protocol for reason specified by investigator other than route, side and site. Site and route of vaccination is wrong or unknown Wrong replacement or study vaccine administered (not compatible with the vaccine regimen associated to the treatment number) 	Visit 1, Visit 2
1080	Vaccine temperature deviation	Visit 1, Visit 2
1090	Expired vaccine administered	Visit 1, Visit 2
2010	Protocol violation (inclusion/exclusion criteria)	Visit 1
2040*	Administration of any medication forbidden by the protocol (refer to Section 7.5.2 of the protocol) administered in the period from the first dose of study vaccine and ending at Visit 3 (Day 1 to Month 3)	Visit 1 to Visit 3

Code	Condition under which the code is used	Visit (timepoints) where the code is applicable
2050*	Underlying medical condition forbidden by the protocol Any intercurrent medical condition (IMC) (refer to section 7.6 of the protocol) which can affect the immune response to the study vaccine and ending at Visit 3 (Day 1 to Month 3)	Visit 1 to Visit 3
2060*	Concomitant infection related to the vaccine which may influence immune response	Visit 1 to Visit 3
2070*	Concomitant infection not related to the vaccine which may influence immune response	Visit 1 to Visit 3
2080	Subjects did not comply with vaccination schedule DOSE 1 – DOSE 2 = 49-83 days	Visit 2
2090	Subjects did not comply with blood sample schedule DOSE2 - blood sample (BS)2 = 28-48 days	Visit 3
2100	Serological results not available post-vaccination CCI [REDACTED]	Visit 3
2120	Obvious incoherence or abnormality or error in data CCI [REDACTED]	Visit 3
2500	Subjects who didn't receive two doses	Visit 2
3500	Subjects having confirmed HZ episode prior to 30 days after the dose 2	Visit 1 to Visit 3
2130	CCI [REDACTED]	[REDACTED]

*Attribution of these elimination codes to subject need CRDL review of individual listing

** Attribution of these elimination codes will be evaluated on case-by-case basis and requires CRDL confirmation

#CCI [REDACTED]

4.2.5. Elimination from unsolicited and solicited safety set

Unsolicited and solicited safety set is not applicable for the study.

5. STATISTICAL ANALYSES

The standard data derivation rules and stat methods are described in section 10.1 while the study specific data derivation rules and stat methods are described in section 9 of the SAP.

Analysis on Covid-19 cases has been added in the analysis of safety section of the SAP.

5.1. General Considerations

Note: Subject-level data will be available interactively via RAPIDO DV after AAC.

5.2. Subjects Disposition

Number of enrolled and vaccinated (at least 1 vaccination) subjects, included in each group or in total for a given age category or for all age categories will be described.

5.3. Demography

5.3.1. Analysis of demographics/baseline characteristics planned in the protocol

Demographic and other baseline characteristics will be described by assigned group and for the total for ES and mES and the **CCI** [REDACTED].

Demographic characteristics (age at first study vaccination in years, gender, race and ethnicity) will be summarized overall and by study groups using descriptive statistics:

- Frequency tables will be generated for categorical variables such as center.
- Mean, standard deviation, median, minimum and maximum will be provided for continuous data such as age.

Cohort description and withdrawal status will be summarized by group and overall. All important protocol deviations leading to elimination will be presented.

All the above analyses will be performed by age strata (50-69 YOA and ≥ 70 YOA) on ES and mES.

5.3.2. Additional considerations

Following additional tables will also be generated:

- Number of subjects by centers will be presented on ES.
- ***Deviation from protocol-defined age and visit interval on ES.***
- The following table will be generated for web disclosure:
 - Percentage of enrolled subjects by age categories (18-64, 65-84, ≥ 85) YOA will be tabulated by group.
- Summary of important protocol deviations leading to elimination from any analysis will be presented for the Enrolled Set overall and by age strata.
- The number of subjects enrolled into the study as well as the number of subjects excluded from ***mES and PPS*** analyses will be presented through 3 consort tables, overall and by age strata only for Consort table 1 and 2:
 - Consort table 1 - Showing the subjects disposition from Enrolled Set to ES
 - Consort table 2 – Showing the subjects disposition from ES to mES
 - Consort table 3 - Showing the subjects disposition from ES to PPS

5.4. Exposure

5.4.1. Analysis of exposure planned in the protocol

None

5.4.2. Additional considerations

The number of doses administered will be tabulated. The number of doses administered will be tabulated by age stratum.

5.5. Efficacy/Effectiveness

The primary analysis of efficacy will be based on the mES. A secondary analysis based on the ES will be performed to complement the mES analysis.

5.5.1. Analysis of efficacy planned in the protocol

5.5.1.1. Primary Objective

The primary inferential analysis of efficacy on the mES will be based on the occurrence of the primary endpoint anytime from 30 days after the administration of the second dose of the study vaccine up to study end. All subjects from the mES will contribute to the comparison.

It will consider the exact inference on the relative risk (RR) adjusted for age strata conditionally to the total number of HZ cases observed and time at risk. This method computes an exact CI around the rate ratio (ratio of the event rates in the RZV group versus control group) and takes into account, the sum of the time at risk of the subjects within each group.

Incidence rate and VE with 95% CI will be calculated using Poisson method. The VE will be defined as 1 minus the RR. RR is defined as the ratio of the incidence rates of the RZV group over the placebo group [VE= (1 – RR) x 100]

The VE of RZV against HZ will be demonstrated if the LL of the two-sided 95% CI of VE is above 25%. All p-values reported will be related to the null hypothesis test $VE = 0$.

The calculation of the time at risk and other statistical method detail are provided in Section 9.2.1.

5.5.1.2. Secondary Objective

The number of confirmed HZ cases, follow-up days, associated rate, VE with 95% CI will be presented by each age category, descriptively, as for the primary endpoint.

5.5.2. Additional considerations

Following descriptive table and figure will be generated by study groups on mES and ES:

- For each study group, the number of subjects at risk, person-year, number and incidence of confirmed HZ will be tabulated overall.
- Forest plot for vaccine efficacy against HZ by age strata and overall during the entire study period
- ***Cumulative incidence curve for HZ for each study group.***
- Number and percentage of episodes of all confirmed HZ episodes during the entire study period.
- Number and percentage of confirmed HZ episodes out of all the suspected cases reported.
- Number and percentage of suspected cases for which at least one PCR sample was collected on ES only.
- Distribution of suspected HZ cases using the HZ classification tools (PCR testing & HZ Ascertainment Committee (HZAC))
- The vaccine efficacy will be assessed by Poisson method for primary objective and fitted via the PROC GENMOD procedure according to the following code

```
PROC GENMOD DATA=pois_ve EXACTONLY;  
BY AGECAT;  
STRATA AGECAT;  
CLASS AGECAT/PARAM=ref;  
MODEL nb_cases = group_nb/DIST=poisson OFFSET = Log_T LINK=log;  
EXACT group_nb /ESTIMATE OUTDIST=dist ALPHA=0.05;  
ODS OUTPUT ExactParmEst=estimate ExactTests=ExactTest;  
RUN;
```

Where,

nb_case = number of cases

[figure not shown]
agecat = Age strata categories (50-69 and \geq 70 YOA)

group_nb = Group information of the subject (treatment received by subject)

Log_T = Log of the follow-up time

```
DATA VE ;  
SET ESTIMATE;  
FORMAT VE best12. ll best12. ul best12.;  
VE = ( 1 - exp (estimate)) * 100;  
ll = ( 1 - exp (UPPERCL)) * 100;  
ul = ( 1 - exp (LOWERCL)) * 100;  
RUN;
```

CCI

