Primary	
Confirmed HZ cases for efficacy
 
The primary analysis of efficacy on the mES will be based on the occurrence of the primary endpoint anytime from 30 days after the administration of the second dose of the study vaccine up to study end. All subjects from the mES will contribute to the comparison.
 
It will consider the exact inference on the relative risk adjusted for age strata conditionally to the total number of HZ cases observed and time at risk. This method computes an exact CI around the rate ratio (ratio of the event rates in the vaccinated versus control group) and takes into account the sum of the time at risk of the subjects within each group.
 
Incidence rate and VE with 95% CI will be calculated. The VE will be defined as 1 minus the relative risk (RR). RR is defined as the ratio of the incidence rates of the vaccine group over the placebo group
 
VE= $(1 - \text{relative risk}) \times 100$
 
The VE of RZV against HZ will be demonstrated if the LL of the two-sided 95% CI of VE is above 25%. All p-values reported will be related to the null hypothesis test VE = 0.
 
The CI for VE will be derived from the exact CI from RR [Miettinen, 1985].

Secondary	
Confirmed HZ cases during the study in each age category (Descriptive)
 
The number of confirmed HZ cases, follow-up days, associated rate, VE with 95% CI will be presented by each age category, descriptively, as for the primary endpoint.

CCI

CCI

Endpoint	Statistical Analysis Methods
Exploratory	CCI

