6. ANALYSIS INTERPRETATION

The primary objective of VE in the prevention of HZ compared to placebo in Chinese adults \geq 50 YOA, as measured by the reduction in HZ risk is considered met if the LL of the 2-sided 95% CI of VE is above 25%.

For all secondary objectives, analyses will be descriptive with the aim to characterize the differences in reactogenicity, safety and immunogenicity between groups.

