8. CHANGES TO THE PROTOCOL DEFINED STATISTICAL ANALYSIS

Following is the change from protocol defined statistical analysis:-

- Fatal SAEs will not be tabulated using the date of death within the same time periods.
- **CC1**
- *Grade 3 for redness/swelling will be defined as redness/swelling with diameter ≥ 100 mm in Chinese scale*
- *Preferred Terms to identify Grade 4 for swelling and redness have been added*
- *The analysis on at least 1 local AE (solicited and unsolicited; solicited only) with at least 1 general AE (solicited and unsolicited; solicited only) and with any AE (solicited and unsolicited; solicited only) during the solicited follow-up period with causal relationship with vaccine and AE rated as at least grade 3 according to GSK and Chinese scale will not be performed.*

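### The only efficacy code in the SAP, labelled for the primary objective, runs separately by age group and so does not return the single age-adjusted VE that the success criterion applies to

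*SAP*

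**What the plan says.** The two documents describe the primary efficacy method in almost the same words. SAP 5.5.1.1 calls for "exact inference on the relative risk (RR) adjusted for age strata conditionally to the total number of HZ cases observed and time at risk", and protocol 10.3.3.1 for "exact inference on the relative risk adjusted for age strata conditionally to the total number of HZ cases observed and time at risk". SAP 5.5.1.1 adds that every mES subject contributes to the comparison and that efficacy is shown if the lower limit of the two-sided 95% CI exceeds 25%. SAP 6 repeats that criterion for adults aged 50 and over.

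The age-specific results are a different objective. Under SAP 5.5.1.2, "VE with 95% CI will be presented by each age category, descriptively, as for the primary endpoint", and SAP 6 says: "For all secondary objectives, analyses will be descriptive".

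SAP 5.5.2 then gives the only efficacy code in the plan, introduced by "The vaccine efficacy will be assessed by Poisson method for primary objective and fitted via the PROC GENMOD procedure according to the following code". The PROC GENMOD call contains BY AGECAT and STRATA AGECAT. The model has treatment group as its only term and log follow-up time as offset, and the notes define AGECAT as 50-69 and ≥70. The same section plans a "Forest plot for vaccine efficacy against HZ by age strata and overall during the entire study period". The SAP document history records the code edit in Amendment 1: "Updated model of vaccine efficacy: added by agecat statement and removed agecat from model".

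**The concern.** A BY statement makes the procedure fit the model once per level of the BY variable. Within each of those fits AGECAT is constant, so stratifying on it adjusts for nothing. The exact-estimates table, and the data step that converts it to VE, would hold one row per age group and no overall row. That is the descriptive secondary analysis of SAP 5.5.1.2 printed under the primary-objective label.

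The trial has one confirmatory criterion. Someone who runs the printed code does not obtain the estimate to which it applies. The overall VE has to come from code the SAP does not show, and whether that code is stratified or unadjusted is then settled outside the printed specification. The printed code also cannot fill the overall row of the planned forest plot.

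**Working it through.** **1. The plan's power figure belongs to one overall test.** Inputs from protocol 10.1 and 10.1.2: VE 85%, margin 25%, 27 cases, 1:1 allocation, one-sided alpha 2.5%, attack rate 0.85% per year, 2762 evaluable per group.

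- Expected placebo cases: 2762 × 0.0085 = 23.5. RZV: 23.5 × 0.15 = 3.5. Total 27.0.
- RZV share of cases at the margin: p0 = 0.75/1.75 = 0.4286. Under VE 85%: p1 = 0.15/1.15 = 0.1304.
- Exact binomial test with n = 27: reject at 6 or fewer RZV cases (attained alpha 0.0216). Power is 94.65%.

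This agrees with the plan's statement of at least 90% power, for a single test on all 27 cases.

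**2. Required analysis against printed code, on the same data.** Assumptions: 27 cases (the planned minimum), 4 of them in RZV, equal person-time, and an age split of 21 (3 RZV) and 6 (1 RZV).

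For a single group, the Clopper-Pearson limits on the RZV share p convert by VE = 1 − p/(1 − p). For the age-stratified analysis, the total RZV count T is the sum of two binomials (n = 21 and 6) with p_i = RR·r_i/(1 + RR·r_i), where r_i is the RZV:placebo person-time ratio in stratum i. The limits for RR solve P(T ≤ 4) = 0.025 and P(T ≥ 4) = 0.025.

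| Analysis | RZV cases / all cases | VE | 95% CI |
|---|---|---|---|
| Unadjusted overall | 4/27 | 82.6% | 49.1 to 95.6 |
| STRATA, no BY (as the text requires) | 4/27 | 82.6% | 49.1 to 95.6 |
| Printed code, 50-69 | 3/21 | 83.3% | 42.9 to 96.9 |
| Printed code, ≥70 | 1/6 | 80.0% | -78.7 to 99.6 |

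**3. Stratified against unadjusted overall run.** At equal person-time the two coincide. For unequal person-time, assume 77.5% of placebo person-time is in 50-69 and the ratios r_i differ in opposite directions. The pooled ratio is then 0.775 × 0.95 + 0.225 × 1.05 = 0.9725, or 1.0275 with the ratios reversed. Lower limits, stratified / pooled:

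| Ratios (50-69, ≥70) | 21/6 case split | 17/10 case split |
|---|---|---|
| 0.95, 1.05 | 47.62 / 47.66 | 48.40 / 47.66 |
| 1.05, 0.95 | 50.46 / 50.46 | 49.72 / 50.46 |

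The largest gap in these four scenarios is 0.74 points.

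**4. If the 25% limit were read off the printed output.** The same exact test was averaged over a Binomial(27, s) number of cases in ≥70, with VE 85% in both strata.

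| Share of cases in ≥70 (s) | Power, 50-69 | Power, ≥70 |
|---|---|---|
| 20% | 83.1% | 9.9% |
| 25% | 79.6% | 18.4% |
| 40% | 67.8% | 43.3% |

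The shares of 20-25% are the enrolment targets; 40% is a further assumption. With six cases in ≥70, even 0 in RZV gives a lower limit of 15.1%, so 25% is out of reach.

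**The case against.** The best defence is that nothing confirmatory is in doubt. SAP 5.5.1.1 and 6 tie the 25% limit to the overall VE, the age-specific results are descriptive, protocol 10.1.2 assigns the 27 cases to the overall analysis, and the forest plot needs an overall row. The code stands last in a list of supplementary outputs. With BY and STRATA side by side, it may be one template meant for both purposes. A missing overall row would be noticed, and table layouts are held in a separate document. An overall run without stratification would hardly move the lower limit. The stratum power figures describe a test the plan does not make.

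Most of this stands, and it limits the weight of the point. The decision rule is sound, and the figures in step 4 show only what a misreading would cost. It does not remove the error. The code is labelled for the primary objective, and no other efficacy code is printed. As written it cannot return the required estimate. A stacked overall level of AGECAT, which the SAP does not define, would not help either: under BY that run would be unadjusted for age, contrary to both documents.

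SAP 8, headed "Following is the change from protocol defined statistical analysis", shows no change to the primary efficacy analysis among its readable entries. Little follows from that, because one entry is redacted and the protocol method is restated unchanged in SAP 5.5.1.1. It means only that nothing readable there supports replacing the overall estimate.

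**Conclusion.** The concern holds as a conflict between code and text that should be fixed before the final analysis; the estimand and the success rule are not undefined. In the illustration, the required result is one VE with 95% CI 49.1 to 95.6, and the printed call returns two intervals, 42.9 to 96.9 and -78.7 to 99.6. The choice between a stratified and an unadjusted overall run matters little: 0 to 0.74 points on the lower limit in the scenarios tried. The harm therefore lies in pre-specified code that yields the wrong analysis, and a materially different overall VE is not expected.

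That the printed call gives two age-specific results follows from the code alone. The sizes rest on assumed case counts, age splits and person-time ratios.

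**What to change.** Print two calls in SAP 5.5.2, each with its own label.

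- **Primary objective** (mES, repeated on the ES as the complementary analysis): delete BY AGECAT, and keep STRATA AGECAT and the EXACT statement for group_nb. This gives one age-stratified exact relative risk and CI. State that the 25% criterion applies to this output only.
- **Secondary objective**: keep BY AGECAT and drop STRATA. Label it as the descriptive per-age analysis of SAP 5.5.1.2.

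State which call feeds the overall row of the forest plot and which feeds the age rows. The cost is a few lines of SAP code, with no extra data and no protocol change.
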